4.5 Sample Size Calculation

Sample size calculation has been based on the primary outcome variable (prevalence of peri-implant diseases). Previous studies have observed a patient-level prevalence of peri-implant diseases of 24%. Our hypothesis is that the prevalence of peri-implant diseases is higher when the inter-implant distance is reduced, around 44%. Accepting an alpha risk of 5% and a beta risk of 20% in a two-sided test, a total of 180 patients with adjacent dental implants (90 patients in each group) are required. Therefore, 90 patients will be recruited at each center. A loss rate of 12% has been

estimated.

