4. MATERIAL AND METHODS

4.1 Study Design

The present research project has been designed as a multicentric cross-sectional study. The STROBE guidelines have been followed in the design of this observational study.

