4.3 Study population

Subjects will be selected from an electronic database collected at the CUO (UIC) / CU (FMDUL) and composed of patients treated with at least two contiguous dental implants before 2021. This investigation will use a stratified random sampling based on year of implant placement to select a representative sample of subjects with implant-supported restorations conducted during the period 2001–2020 at the CUO and CU. Then, two examiners ([name]) will contact patients by telephone

once every 2 days (with a maximum of 3 attempts) for an evaluation by the same investigators ([name]).

Criteria for subject selection will be as follows:

- The patient must be ≥ 18 years of age and systemically healthy;
- Partially edentulous patients, rehabilitated until 2020 (i.e., a minimum of 3 years of function time) with at least two contiguous implant-supported restorations in the maxilla or mandible;
- Screw or cemented-retained prosthesis;
- Fixed dental prosthesis (i.e., single crowns and partial prosthesis);
- No implant mobility.

Moreover, the exclusion criteria will be the following:

- Pregnant and lactating women;
- Patients who have taken systemic antibiotics during the 3 months prior to the examination;
- Patients being treated with drugs that may induce a gingival overgrowth;
- Patients undergoing orthodontic treatment (since it can influence periodontal diagnosis);
- Patients who have received mechanical debridement during the 3 months prior to the exam;
- Patients who have received surgical treatment for peri-implantitis;
- Psychophysical inability to carry out study procedures.

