4.4 Study Groups

Patients who meet the selection criteria will be included in the study and will be classified based on the inter-implant distance:

Group 1: Inter-implant distance ≤ 3 mm

Group 2: Inter-implant distance > 3 mm

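### Section 4.5 recruits the 180 patients it needs, then estimates an undefined 12% loss (power about 76% if it falls on the 180), and 90 per centre does not secure 90 per distance group

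*Combined protocol and SAP*

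**What the plan says.** Section 4.5 sets the error rates ("Accepting an alpha risk of 5% and a beta risk of 20% in a two-sided test"), takes 24% as the reference prevalence from earlier studies, and expects about 44% where the distance is reduced. It concludes that "a total of 180 patients with adjacent dental implants (90 patients in each group) are required". The next sentences turn this into a recruitment target and add a loss: "Therefore, 90 patients will be recruited at each center. A loss rate of 12% has been" estimated. Nothing in 4.5 says what counts as a loss, or whether 180 is the number before or after it.

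Three other sections bear on this:

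- Section 4.1: "The present research project has been designed as a multicentric cross-sectional study".
- Section 4.3: "This investigation will use a stratified random sampling based on year of implant placement". Sampled patients are then contacted by telephone, with up to three attempts.
- Section 4.4: "Patients who meet the selection criteria will be included in the study and will be classified based on the inter-implant distance", with 3 mm as the cut-off. No quota for either group is given.

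**The concern.** There are two separate problems in one short paragraph.

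First, the number required and the number recruited are both 180, yet a 12% loss is expected. If the loss falls on those recruited, fewer than the required number will be analysed. If it falls earlier, on patients who are invited but never attend, the 180 is untouched. The text does not say which.

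Second, the calculation assumes 90 patients in each distance group, and the recruitment sentence converts this into 90 at each centre as if one followed from the other. Centre and distance group divide the sample in different ways. Patients are sampled by year of placement and sorted by distance afterwards, so the group sizes are an outcome of the study.

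At stake is whether the stated 20% beta risk for the primary outcome holds. If it does not, a null result would be harder to interpret than the plan suggests.

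**Working it through.** **Inputs (4.5):** p1 = 0.24 (> 3 mm), p2 = 0.44 (≤ 3 mm), difference d = 0.20, two-sided alpha 0.05 (z = 1.960), power 80% (z = 0.842), equal groups, loss 12%. Mean prevalence 0.34.

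**Step 1: reproduce the 180.** With pooled variance under the null and unpooled under the alternative,

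n = [1.960·√(2·0.34·0.66) + 0.842·√(0.24·0.76 + 0.44·0.56)]² / 0.20²
= [1.960·0.670 + 0.842·0.655]² / 0.04 = 86.9, so 87 per group (174 in total).

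Other uncorrected two-sided formulas give 85 (unpooled), 87 (arcsine) and 89 (pooled throughout) per group, or 170 to 178 in total. So 90 per group is a slightly rounded-up requirement with no loss in it.

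**Step 2: could 180 already contain the 12%?** Dividing the unrounded results by 0.88:

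| Formula | n per group | n / 0.88 |
|---|---|---|
| Unpooled | 84.1 | 95.6 |
| Arcsine | 86.3 | 98.0 |
| Pooled/unpooled | 86.9 | 98.7 |
| Pooled throughout | 88.1 | 100.1 |

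None gives 90 at the stated prevalences. A continuity-corrected formula needs more (97 per group before any loss).

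**Step 3: power with and without the loss.** Power = Φ[(d·√n − 1.960·0.670) / 0.655], n per group.

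- n = 90: (1.897 − 1.313)/0.655 = 0.892, power 81.4%.
- n = 87: 80.1%; n = 86: 79.6%. The tolerable loss is 1 − 87/90 = 3.3%.
- 12% lost: 180 × 0.88 = 158.4, so 79 per group. (1.778 − 1.313)/0.655 = 0.710, power 76.1%.

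Exact enumeration of the uncorrected chi-square gives 81.7% at 90 per group and 76.9% at 79.

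**Step 4: unequal distance groups.** The documents give no distribution of distances, so these splits are assumptions. For group sizes a (≤ 3 mm) and b (> 3 mm), with p̄ = (0.44a + 0.24b)/(a + b),

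power = Φ{[0.20 − 1.960·√(p̄(1−p̄)(1/a + 1/b))] / √(0.44·0.56/a + 0.24·0.76/b)}.

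| Split | 180 evaluable (≤ 3 / > 3 mm) | 158 evaluable (≤ 3 / > 3 mm) |
|---|---|---|
| 50:50 | 90/90: 81.4% | 79/79: 76.1% |
| 40:60 | 72/108: 80.3%; 108/72: 79.4% | 63/95: 75.0%; 95/63: 73.8% |
| 30:70 | 54/126: 75.7%; 126/54: 73.2% | 47/111: 70.1%; 111/47: 67.0% |
| 20:80 | 36/144: 65.5%; 144/36: 60.1% | 32/126: 60.6%; 126/32: 54.5% |

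With 180 evaluable, power is at least 80% from 71/109 to 104/76, that is, with about 39% to 58% of patients in the ≤ 3 mm group.

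**The case against.** The strongest reply is that 180 may already include the loss. The plan says around 44% and names no formula. At 24% versus 45%, the formula in step 1 needs 79.2 per group, and 79.2/0.88 is about 90. This is a real possibility, but it departs from the stated prevalence, and the wording runs from a number required to the same number recruited. If this is what was done, 4.5 should say so.

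The second reply is that the design leaves little room for loss after enrolment: there is a single examination, and in 4.7 probing follows consent directly. Non-attendance after the telephone call is a plausible meaning, and then 180 examined patients keep about 81% power with equal groups. This stands, and it is why the 76% is conditional. Even on the worse reading, the shortfall is only about 4 points below 80%.

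The third is that 90 per centre merely divides 180 between two sites, and that an observational study does not normally fix its exposure split. That is fair, and a 40:60 split costs only 1 to 2 points. But the stated requirement is 90 per distance group, and nothing visible delivers it or gives an expected split.

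Finally, the available text goes from 4.7 to 4.11, so a definition of loss in between cannot be excluded. It would not change the point about centres and groups.

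**Conclusion.** The concern holds. On its own inputs, 180 is an adequate evaluable number with a margin of about 3%, against a stated loss of 12%. Power is about 76% if the loss comes out of the 180 recruited and 81% if 180 are examined, both with equal groups; the plan does not say which applies. The gap from loss alone is modest and would close if the true prevalence at short distances were about 45%.

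The group split does not depend on how loss is defined. Its effect is small at 40:60 and larger than that of the loss at 20:80, but the actual split is unknown until distances are measured. All power figures assume the chi-square test without continuity correction; with the correction they are lower (about 77% at 90 per group and 70-71% at 79). This should be fixed, but it does not invalidate the study.

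**What to change.** Reword 4.5 in three places.

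1. Define the loss, choosing whichever was meant:
   - *Loss is non-response before enrolment; 180 patients will be examined, giving 81% power with equal groups.*
   - *Loss is an enrolled patient without an evaluable outcome; about 158 evaluable patients are expected, giving about 76% power for 24% versus 44% with equal groups, or 80% for 24% versus about 45%.*
2. Remove the inference from group to centre, and present 90 per group as a planning assumption: *The calculation assumes equal distance groups. Each centre will enrol 90 patients; the size of each distance group will depend on the distances observed.*
3. State power for 50:50, 40:60 and 30:70 splits: 81%, 79-80% and 73-76% with 180 evaluable, or 76%, 74-75% and 67-70% with 158.

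This costs a rewritten paragraph and a slightly less favourable stated power. Sampling, groups, analysis and patient numbers do not change. If the sponsor prefers to secure 180 evaluable patients after a 12% loss, 180/0.88 = 204.5, so about 205 would have to be recruited. That is a larger commitment, is not needed to make 4.5 accurate, and would not by itself balance the distance groups.

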4.7 Data collection

Two calibrated investigators will consecutively call patients for an appointment and will be responsible of enrolling the patients.

The study variables will be recorded in a case report form (CRF) specially designed for the study. Each study patient will be assigned a numerical code comprising a 3-digit patient code (assigned correlatively as they are included in the study). Only the study investigators will be able to identify the patient by their code.

Medical history of the patients will be reviewed. Patients will also be advised of their role in this study and asked to sign an informed consent. After giving consent, patients will undergo a full-mouth manual probing using a periodontal probe PCP-UNC 15 (HuFriedy®, [name]) to determine their periodontal and peri-implant status and, if necessary, a full-mouth periapical radiographic examination will be performed.

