4.11 Statistical analysis

The Shapiro-Wilk test will be used to determine if the data follow a Gaussian distribution. Descriptive statistics will be expressed as mean \pm standard deviations (SD), median or percentage for parametric, non-parametric and categorical data, respectively.

Comparisons between study groups will be performed using Chi-square test (Fisher's exact test with observed frequencies <5) for categorical variables while continuous variables will be tested using Student's T test (Mann Whitney U test in variables that are not normally distributed). For ordinal variables, the linear relationship will be calculated using Kendall's tau coefficient.

A final logistic regression model will be performed including the prevalence of peri-implant diseases as a dependent variable. The study group and other potential cofactors will be included as independent variables.

Intra- and inter-examiner reproducibility will be calculated with the intraclass correlation coefficient.

A p-value <0.05 will be considered statistically significant. R Studio software will be used for all analyses.

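### Section 4.5 states 80% power on 90 patients per distance group, but the visible plan fixes only the total of 180, which does not appear to allow for the 12% loss

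*Combined protocol and SAP*

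**What the plan says.** Section 4.5 takes prevalences of 24% and, with reduced distance, about 44%. It sets the error rates: "Accepting an alpha risk of 5% and a beta risk of 20% in a two-sided test". It then gives the size and the recruitment target: "a total of 180 patients with adjacent dental implants (90 patients in each group) are required. Therefore, 90 patients will be recruited at each center". The section closes with a loss allowance, "A loss rate of 12% has been" estimated, and does not say whether the 180 already contains it.

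Three other sections bear on how the distance groups arise:

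- Section 4.3: "This investigation will use a stratified random sampling based on year of implant placement to select a representative sample of subjects". The only stratum named is the year.
- Section 4.4: "Patients who meet the selection criteria will be included in the study and will be classified based on the inter-implant distance". The two groups are ≤ 3 mm and > 3 mm.
- Section 4.7: "Two calibrated investigators will consecutively call patients for an appointment and will be responsible of enrolling the patients".

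None of these gives an expected share of patients at ≤ 3 mm, or a target or stopping rule by distance. The supplied text goes from section 4.7 to section 4.11, so sections 4.8 to 4.10 could not be read.

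**The concern.** The comparison that the study is sized for is between distance groups, and its power depends on how many patients are analysed in each. Section 4.5 states those numbers as a requirement. In the visible text, however, the group sizes result from whom the sampling happens to reach, and no expected split is offered in support of 1:1. The 12% loss adds a second uncertainty: if it comes out of the 180, the calculation is short even with perfect balance.

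What is at stake is how a non-significant result would be read. The plan invites the reader to attach a 20% risk of having missed a 20-point difference. That figure holds only near 1:1 and only if nearly all 180 patients are analysed, and the section states neither condition.

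**Working it through.** **Inputs.** From section 4.5: p1 = 0.44 (taken as ≤ 3 mm), p2 = 0.24 (taken as > 3 mm), two-sided alpha 0.05, power 0.80, N = 180, loss 12%. From section 4.11: a chi-square comparison of groups, computed here without continuity correction. Assumed, because the documents give no figure: the share f of patients in the ≤ 3 mm group.

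**1. Reproducing the plan's figure at 1:1.** (1.960 + 0.842)² = 7.849, and the squared difference is 0.20² = 0.04.

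- Pooled variance: 2 × 0.34 × 0.66 × 7.849 / 0.04 = 88.1, so 89 per group.
- Pooled under the null, separate under the alternative: (1.960 × √0.4488 + 0.842 × √0.4288)² / 0.04 = 86.9, so 87 per group.
- Unpooled: (0.44 × 0.56 + 0.24 × 0.76) × 7.849 / 0.04 = 84.1, so 85 per group.

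The stated 90 per group agrees with these to within a few patients, before any loss.

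**2. Does 180 include the loss?** Dividing the unrounded results by 0.88 gives 84.1 / 0.88 = 95.6 up to 88.1 / 0.88 = 100.1, that is about 96 to 101 per group. Ninety fits the figure before loss. If the loss comes out of the 180, 180 × 0.88 = 158.4, so about 158 are analysed.

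**3. Power formula.** With n1 = fN, n2 = (1 − f)N and p̄ = f × 0.44 + (1 − f) × 0.24,

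power = Φ{[0.20 − 1.960 × √(p̄(1 − p̄)(1/n1 + 1/n2))] / √(0.2464/n1 + 0.1824/n2)}.

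- 90/90: (0.20 − 0.1384) / 0.0690 = 0.892, power 81.4%.
- 79/79: (0.20 − 0.1477) / 0.0737 = 0.710, power 76.1%.

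**4. Power over assumed splits.** Where two figures are shown, the first is for the ≤ 3 mm group being the smaller and the second for it being the larger.

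| Split | 180 analysed | 158 analysed |
|---|---|---|
| 50:50 | 81.4% | 76.1% |
| 40:60 | 80.3% / 79.4% | 75.0% / 73.8% |
| 30:70 | 75.7% / 73.2% | 70.3% / 67.3% |
| 20:80 | 65.5% / 60.1% | 60.2% / 54.1% |

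With 180 analysed, power is at least 80% for f from about 0.39 to 0.58. With 158, the maximum is 76.1%, at f of about 0.48, so no split reaches 80%.

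Exact enumeration of the uncorrected chi-square test with 180 analysed agrees closely: 81.7% at 90/90, 74.8% / 73.4% at 30:70, and 65.5% / 61.5% at 20:80.

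**The case against.** **The recruitment sentence is sound.** A reader might infer that the plan confuses centre with distance group because both numbers are 90. The text does not support that: 180 divided by two centres is 90, and the step from the total is correct. The point concerns only what that step leaves open.

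**A quota may exist.** Section 4.5 does state 90 per group as a requirement, and sections 4.8 to 4.10 are not visible, so it cannot be said that the plan has no distance quota. This stands, and it is why the fix asks a question. Sections 4.3 to 4.5, where such a rule would normally appear, are visible and contain none.

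**The uneven splits are assumed.** This also stands. No document supports 30:70 or 20:80, and at 40:60 the cost is only one to two points. A reader might infer that the study is underpowered because the groups will be unbalanced; the documents do not show that.

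**The loss is a separate matter and is unclear in a cross-sectional study.** It is logically separate from the split, and the 12% might mean non-attendance or unusable records. But it bears on the same stated power, and its effect does not depend on an assumed split. Since the section does not settle it, the 76% is conditional.

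**Realised group sizes and confidence intervals will be known at reporting.** True, and this limits the harm. It does not make the planned figure correct as stated.

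**Conclusion.** The concern holds in a limited form. Section 4.5 states a group size and power that the visible design does not secure. No shortfall is demonstrated.

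If all 180 are analysed, the loss of power is negligible at 40:60, about 5 to 8 points at 30:70 (81.4% to between 75.7% and 73.2%), and about 16 to 21 points at 20:80 (81.4% to between 65.5% and 60.1%). If the 12% is taken from the 180, power is about 76% at best. The 85 to 89 per group needed before loss makes this second reading plausible, though the text does not confirm it.

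These figures rest on 24% and 44% being the true prevalences in the > 3 mm and ≤ 3 mm groups, on a two-sided 5% test without continuity correction, and on the splits shown.

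**What to change.** In section 4.5:

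1. State whether 90 per distance group is a recruitment quota or an expectation. If a rule stands elsewhere in the protocol, refer to it.
2. State whether the 12% loss comes out of the 180. If it does, restate the power as about 76% at 1:1.
3. If there is no quota, say that the 80% figure holds only near 1:1, and restate the power for the split expected from clinic records. If that split is unknown, give a range and label the splits as assumed, for example 81% at 50:50 down to 60% at 20:80 with 180 analysed, or 76% down to 54% with 158.

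The cost is a few sentences. No added enrolment or change to the sampling is needed. Section 4.3 does not say that the databases record inter-implant distance; if they do not, an expected split would mean measuring existing images at both centres, and reporting the range avoids that work. The downside is that the stated power may fall below 80%.

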4.6 Researchers training

All participating researchers will attend two training and calibration online meetings. The main aims of these meetings will be to review the objectives of the study and the protocol, standardize case selection, and data collection process.

4.7 Data collection

Two calibrated investigators will consecutively call patients for an appointment and will be responsible of enrolling the patients.

The study variables will be recorded in a case report form (CRF) specially designed for the study. Each study patient will be assigned a numerical code comprising a 3-digit patient code (assigned correlatively as they are included in the study). Only the study investigators will be able to identify the patient by their code.

Medical history of the patients will be reviewed. Patients will also be advised of their role in this study and asked to sign an informed consent. After giving consent, patients will undergo a full-mouth manual probing using a periodontal probe PCP-UNC 15 (HuFriedy®, [name]) to determine their periodontal and peri-implant status and, if necessary, a full-mouth periapical radiographic examination will be performed.

4.11 Statistical analysis

The Shapiro-Wilk test will be used to determine if the data follow a Gaussian distribution. Descriptive statistics will be expressed as mean \pm standard deviations (SD), median or percentage for parametric, non-parametric and categorical data, respectively.

Comparisons between study groups will be performed using Chi-square test (Fisher's exact test with observed frequencies <5) for categorical variables while continuous variables will be tested using Student's T test (Mann Whitney U test in variables that are not normally distributed). For ordinal variables, the linear relationship will be calculated using Kendall's tau coefficient.

A final logistic regression model will be performed including the prevalence of peri-implant diseases as a dependent variable. The study group and other potential cofactors will be included as independent variables.

Intra- and inter-examiner reproducibility will be calculated with the intraclass correlation coefficient.

A p-value <0.05 will be considered statistically significant. R Studio software will be used for all analyses.

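### Section 4.11 lets a Shapiro-Wilk result choose between equal-variance Student's t and Mann-Whitney; if group sizes and spreads both differ, the secondary continuous comparisons can drift from 5%, and Welch's t avoids this at almost no cost

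*Combined protocol and SAP*

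**What the plan says.** Section 4.11 (Statistical analysis) opens with the normality check: "The Shapiro-Wilk test will be used to determine if the data follow a Gaussian distribution". For comparisons between the study groups, "continuous variables will be tested using Student's T test (Mann Whitney U test in variables that are not normally distributed"). The threshold for every test is the same: "A p-value <0.05 will be considered statistically significant". The section mentions no Welch correction and no check of variances. It gives no level for the Shapiro-Wilk test and does not say whether that test is run within groups or on the pooled sample. It plans no confidence interval for these comparisons.

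Section 4.4 (Study Groups) explains how the groups arise: "Patients who meet the selection criteria will be included in the study and will be classified based on the inter-implant distance", with 3 mm as the cut. Section 4.5 (Sample Size Calculation) plans 90 patients per group, but fixes recruitment only as 90 per center. Section 4.3 stratifies sampling by year of implant placement, not by distance.

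The primary outcome is the prevalence of peri-implant diseases. It is binary and is analysed by Chi-square or Fisher's exact test and a logistic model.

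**The concern.** Three features of the rule combine.

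- The pooled-variance t keeps its level when variances are equal or group sizes are equal, and loses it when both differ. Distance is observed rather than allocated, and no quota balances the groups, so the plan secures neither condition.
- The preliminary test examines shape. It does not examine variance, which is the assumption that matters for Student's t at this sample size.
- When the check fails, Mann-Whitney compares the ordering of the two distributions and not their means. Which question is answered for a given variable therefore depends on a preliminary p-value.

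At stake are the p-values of the continuous secondary or descriptive comparisons, which could be too small or too large, and a results table in which some rows concern means and others ranks.

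**Working it through.** **Inputs from the documents.** Two-sided 5% level (4.5, 4.11); 90 per group, 180 in total (4.5); Student's t or Mann-Whitney by Shapiro-Wilk (4.11). The documents give no SD for any continuous variable and no expected unequal split.

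**Assumptions.** Splits of 60/120 and 45/135 (total held at 180); SD 1.5 versus 1; Shapiro-Wilk at 5% within each group, with Student's t only if both groups pass.

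**The plan's own figure.** The only calculation stated is for the binary outcome, 24% versus 44% at 80% power. With a mean proportion of 0.34, n = [1.960 × √(2 × 0.34 × 0.66) + 0.842 × √(0.24 × 0.76 + 0.44 × 0.56)]² / 0.20² = (1.313 + 0.551)² / 0.04 ≈ 86.9, so 87 per group. The plan has 90, with power of 81.4%. This fixes the planned split and has no other bearing here. For the continuous tests the plan states only the nominal 5%.

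**Step 1: Student's t by formula.** Under equal means the t statistic is scaled by the wrong standard error. The true variance of the mean difference is V = s₁²/n₁ + s₂²/n₂. The test uses on average P = [((n₁−1)s₁² + (n₂−1)s₂²)/(n₁+n₂−2)] × (1/n₁ + 1/n₂). The rejection rate is approximately 2 × [1 − Φ(1.973 × √(P/V))], where 1.973 is the t critical value on 178 degrees of freedom.

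- 60/120, smaller group more variable: V = 2.25/60 + 1/120 = 0.0458; P = 1.414 × 0.025 = 0.0354; √(P/V) = 0.878; 1.973 × 0.878 = 1.733; rate about 8.3%.
- 60/120, smaller group less variable: V = 0.0354; P = 1.836 × 0.025 = 0.0459; √(P/V) = 1.138; rate about 2.5%.
- 45/135, smaller group more variable: V = 0.0574; P = 1.309 × 0.0296 = 0.0388; √(P/V) = 0.822; rate about 10.5%.
- 45/135, smaller group less variable: V = 0.0389; P = 1.941 × 0.0296 = 0.0575; √(P/V) = 1.216; rate about 1.6%.
- 90/90: V = P = 0.0361; the ratio is exactly 1 and the rate stays at about 5%, whatever the SD ratio.

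**Step 2: the full two-stage rule by simulation.** Equal true means, normal data, thousands of datasets per case; ranges cover repeated runs.

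| Split | SDs | Planned rule | Welch |
|---|---|---|---|
| 90/90 | 1.5 v 1 | 5.1% | about 5% |
| 90/90 | 2 v 1 | 5.4% | 5.1% |
| 60/120 | smaller group 1.5, larger 1 | 8.6–9.1% | about 5% |
| 60/120 | smaller group 1, larger 1.5 | 2.3–2.8% | about 5% |
| 45/135 | smaller group 1.5, larger 1 | 10.6–11.3% | about 5% |
| 45/135 | smaller group 1, larger 1.5 | 1.8–2.1% | about 5% |

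These agree with the formula, so for normal data nearly all of the distortion comes from the pooled variance and hardly any from the switch. If Shapiro-Wilk is run on the pooled sample instead, the four unbalanced rows become, in order, 7.5%, 2.65%, 10.1% and 2.05%.

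**Step 3: sensitivity to the assumptions.** A milder 80/100 split with SD ratio 1.5 gives 6.3% or 3.9%. A 45/135 split with SD ratio 2 gives 15.2% or 1.0%. Equal spread at 60/120 gives 4.8% to 5.6%.

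**Step 4: skewed data.** Gamma data with mean 3.5 in both groups and SD 1.5 versus 1.0, at 90/90: Shapiro-Wilk rejects in 91% of datasets, so Mann-Whitney is almost always used. The planned rule then rejects in 9.2% to 10.1% of datasets, against 4.9% to 5.3% for Welch; Student's t alone also stays near 5%. The two populations have equal means but medians of 3.29 and 3.41. With gamma data of equal spread (SD 1.2 in both groups), the rule gives 4.6% at 90/90 and 5.1% at 60/120, although the switch occurs in about 86% of datasets.

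**The case against.** The best reply is that the plan sets out 90 per group, and at 90/90 with normal data the rule holds its level even when one SD is twice the other. It also holds with equal spreads, whether the groups are unbalanced or the data skewed. That stands: the two-stage choice does not by itself miscalibrate the tests.

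Second, section 4.11 pairs means with parametric data and medians with non-parametric data, and never declares equal means as the null for the latter. In the gamma case the medians do differ, so Mann-Whitney is detecting a real difference. This also stands: the 10% is an error rate only if means are the target. What remains is that the plan leaves the target to be settled by a preliminary p-value.

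Third, both objectives, both hypotheses, the sample size and the final model concern prevalence. The available text names no continuous outcome for analysis; sections between 4.7 and 4.11 are not in it, and nothing can be read into their absence. This limits the importance of the point.

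A reader might infer that this trial's continuous tests will run at 2% to 11%. The documents do not support that: they give no SDs and no expected imbalance, and other assumptions give narrower or wider ranges. Nor do they support the inference that the main conclusion is at risk.

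**Conclusion.** The point holds conditionally and is minor. The plan relies on an equal-variance t test in observed groups whose sizes and spreads it does not control, and guards it with a check that does not address variance. If the split is between 60/120 and 45/135 and the SD ratio is 1.5, a nominal 5% test on normal data runs at about 9% to 11% or about 2% to 3%, depending on which group is more variable. Both the splits and the ratio are assumptions. Separately, for skewed variables with unequal spread, the hypothesis tested moves from means to ordering without having been chosen in advance. The reach is limited to continuous secondary or descriptive comparisons.

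**What to change.** In section 4.11, replace the selection rule with wording such as: continuous variables will be compared between groups with Welch's t test, reporting the mean difference and its 95% confidence interval; no preliminary normality test will select the method; any variable for which a rank-based comparison is preferred will be named before the data are analysed.

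Whether a particular variable is better compared by means or by ranks is the investigators' choice; the correction is to make it beforehand. Medians can still be shown for skewed variables.

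The cost is a sentence or two of text. When variances are truly equal, simulated power for Student's t versus Welch was 80.3% v 80.3% at 90/90, 75.6% v 75.3% at 60/120 and 67.4% v 66.4% at 45/135, a loss of 1 point or less. For heavy-tailed variables Welch gives up some power against a rank test, which is a reason to name such variables in advance.

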3.2 Specific Hypothesis

Tissue level implants (i.e., one-piece implants) placed with an inter-implant distance < 3mm will result in a higher prevalence of peri-implant diseases than bone level implants.

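### Section 4.11 has no method for correlated implants, so the implant-type hypothesis, if tested with one row per implant, would get wrong standard errors; the patient-level comparison of distance groups is not affected

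*Combined protocol and SAP*

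**What the plan says.** Section 4.3 admits patients "with at least two contiguous implant-supported restorations in the maxilla or mandible" and sets no upper limit. Section 4.4 sorts patients, not implants, into two distance groups. Section 4.5 also works in patients: "Previous studies have observed a patient-level prevalence of peri-implant diseases of 24" per cent is the reference figure, and "a total of 180 patients with adjacent dental implants (90 patients in each group) are required".

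The specific objective (2.2) and specific hypothesis (3.2) turn to implant type. The hypothesis is that tissue-level implants "placed with an inter-implant distance < 3mm will result in a higher prevalence of peri-implant diseases than bone level implants". No unit of analysis is named for it.

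Section 4.11 lists chi-square (Fisher for small frequencies), Student's t or Mann-Whitney, Kendall's tau and a final logistic regression, of which it says "The study group and other potential cofactors will be included as independent variables". No GEE, random effect or cluster-robust variance is mentioned. The only intraclass correlation in the section is for examiner reproducibility.

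**The concern.** Implants in one mouth share host, hygiene and maintenance, so their disease outcomes are likely to be correlated. The methods in 4.11, as described, treat each row as independent. That is harmless with one row per patient. The wording of 3.2, however, invites one row per implant: bone-level or tissue-level is a property of the implant, and nothing stops a patient from having both.

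At stake is one of the plan's two stated hypotheses, to be judged at p < 0.05. If implants are counted as independent, a significant result may partly reflect the same patients counted twice. In the opposite configuration, a real difference may be missed. Because the unit is not fixed, the choice between patient rows and implant rows also stays open until the data have been seen.

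**Working it through.** **1. The plan's own figure.** Inputs from 4.5: "Accepting an alpha risk of 5% and a beta risk of 20% in a two-sided test"; prevalence 24% against 44%; 90 patients per group. With the simple pooled-variance formula and mean prevalence 0.34:

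n = 2 × 0.34 × 0.66 × (1.960 + 0.842)² / 0.20² = 88.06, so 89 per group.

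Power at 90 per group is 81.4%. The stated 90 is therefore reproduced as a patient-level number before any allowance for loss. Clustering of implants does not alter it.

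**2. Inputs for the clustering check.**
- Implants per patient, m: at least 2 (4.3). No mean or maximum is given, so m = 2 and m = 3 are shown.
- Within-patient correlation of disease (ICC): not in the documents. Assumed range 0.1 to 0.7.

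**3. Factor shared by all implants of a patient** (for example, the same type at neighbouring sites).
- Design effect: DE = 1 + (m − 1) × ICC
- Naive standard error as a share of the correct one: 1/√DE
- Actual size of a nominal 5% test: 2 × [1 − Φ(1.96/√DE)]

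Example, m = 2 and ICC = 0.3: DE = 1.30; 1/√1.30 = 0.88; 1.96/√1.30 = 1.72; size 8.6%.

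| m | ICC | DE | Naive/correct SE | Size, formula | Size, simulated |
|---|---|---|---|---|---|
| 2 | 0.1 | 1.10 | 95% | 6.2% | 6.5% |
| 2 | 0.3 | 1.30 | 88% | 8.6% | 8.7% |
| 2 | 0.5 | 1.50 | 82% | 11.0% | 11.0% |
| 2 | 0.7 | 1.70 | 77% | 13.3% | 13.3% |
| 3 | 0.1 | 1.20 | 91% | 7.4% | 7.6% |
| 3 | 0.3 | 1.60 | 79% | 12.1% | 12.3% |
| 3 | 0.5 | 2.00 | 71% | 16.6% | 16.8% |
| 3 | 0.7 | 2.40 | 65% | 20.6% | 20.9% |

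The simulation drew beta-binomial outcomes for 90 patients per group at prevalence 0.34, with 20,000 runs. In terms of information, 90 patients with two implants each supply 180 implants, but these are worth 180/DE: about 164, 138, 120 and 106 at ICC 0.1, 0.3, 0.5 and 0.7.

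**4. Factor that differs within the patient.** The general form is DE = 1 + (m − 1) × ICC(outcome) × ICC(factor). With one implant of each type in every patient, ICC(factor) = −1, so for m = 2, DE = 1 − ICC. At ICC 0.5, DE = 0.5, 1.96/√0.5 = 2.77, and the size is about 0.6%. Simulation also gave 0.6% at ICC 0.5, and 3.9% at ICC 0.1. Here the naive standard error is too large.

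The direction of the error therefore depends on how implant type is distributed within patients, which the documents do not describe.

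**The case against.** The strongest reply is that the plan does not describe an implant-level analysis. Section 4.4 classifies patients, 4.5 counts patients from a patient-level prevalence, and the tests in 4.11 compare the study groups, which are groups of patients. With one row per patient, independence holds. This stands for the main comparison. A reader might infer that the 180 patients or the distance-group test is undermined; the documents do not support that. The reply does not settle the implant-type hypothesis, for which no unit is given and for which a patient with both types would need a rule.

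A second reply is that the error need not inflate false positives. This also stands. A reader might infer that any implant-level test would be too liberal, but step 4 of the working shows the reverse when type varies within patients. The documents describe neither a split design nor uniform type within a patient.

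Two limits on the evidence also stand. The text available goes from 4.7 directly to 4.11, so a definition of variables or of the unit in 4.8 to 4.10 cannot be excluded. And no section states that type, retention or probing values are recorded implant by implant; the full-mouth probing in 4.7 makes this plausible, but it is an inference.

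**Conclusion.** The point holds in conditional form. The primary comparison appears to be patient-level and is unaffected if analysed that way; the sample size is not called into question. For the implant-type hypothesis, and for any other outcome analysed with one row per implant, the methods listed in 4.11 would give wrong standard errors.

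If type is shared or positively correlated within patients, the errors are too small. When it is fully shared, a nominal 5% test runs at about 6% to 13% with two implants per patient, and at about 7% to 21% with three. If type differs within most patients, the test is conservative. These sizes rest on an assumed ICC of 0.1 to 0.7 and assumed cluster sizes, since the documents give neither a correlation nor a mean number of implants. What does not depend on the assumed values is that 4.11 states neither the unit nor a method for correlated implants. This should be corrected before analysis.

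**What to change.** In 4.11:

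- Name the patient as the unit for the comparison of distance groups, and restrict chi-square, t and ordinary logistic regression, with the other listed tests, to analyses with one row per patient.
- State how a patient with several inter-implant distances is assigned to a group. Three implants in a row already give two distances, and the supplied text has no rule for this.
- Analyse the implant-type hypothesis, and any other implant-level outcome, by logistic GEE with robust standard errors clustered on patient, or by a mixed logistic model with a patient random intercept. Choose one in advance, because the two give odds ratios with different meanings (population-averaged and patient-specific).

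Either method handles both directions of error. If 4.8 to 4.10 already define the unit, a cross-reference covers that part.

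The cost is a few sentences and standard R routines, with no change to recruitment, examinations or sample size. The downside is that intervals for implant-level results will usually be wider.
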